11.1.1 Documentation of Adverse Events

Adverse events will be collected from the time of informed consent until the last scheduled study follow-up, 4 weeks after the last dose of the study drug, or until the last unscheduled safety-related assessment whichever occurs latest. An AE is any untoward medical occurrence (which does not necessarily have to have a causal relationship with this treatment). An AE can be any unfavorable and unintended sign (including an abnormal laboratory finding, for example), symptom, or disease temporally associated with the use of an investigational product, whether or not related to the study drug. This includes any occurrence that was new in onset or aggravated in severity or frequency from the baseline condition. Planned hospital admissions or surgical procedures for an illness or disease that existed before the patient was screened in the study are **not** to be considered AEs unless the condition deteriorated in an unexpected manner during the study (e.g. surgery was performed earlier than planned).

Abnormal results of diagnostic procedures, including laboratory test abnormalities, are considered AEs if they result in any one of the following:

- Discontinuation of study treatment;
- Require treatment or any other therapeutic intervention;
- The necessity for further diagnostic evaluation (excluding a repetition of the same procedure to confirm the abnormality);
- Association with clinical signs or symptoms that may have a significant clinical impact, as determined by the Investigator.

Patients are encouraged to report AEs spontaneously or in response to general, non-directed questioning. All AEs are to be followed until resolution or until a stable clinical endpoint is reached. The investigator should question patients about AEs and changes in pre-existing illnesses since their last visit and must record the information in the patients' medical records. The onset and end dates, severity, relationship to study agent, action taken, and outcome must be recorded for each AE. All AEs are to be recorded on the appropriate e-CRF and in detail on the source documents.

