Any AE that occurs within 4 weeks following the last dose of the study drug will be considered treatment emergent (TEAe) and must be recorded in the e-CRF and, if an SAE, reported immediately to the Sponsor. Adverse events that are ongoing at the end of the 4-week follow-up period should be marked as ongoing. However, it is the responsibility of the Investigator to follow up on these events until resolution, according to standard medical care.

Any AE or SAE that the investigator becomes aware of outside of the reporting period until the end of the study that has or is believed to have a causal relationship to the study drug should be reported to Laurent

Pharmaceuticals via telephone. Patients who experience AEs will be monitored with relevant clinical assessments and laboratory tests, as determined by the Investigator. All AEs and laboratory abnormalities encountered during the study should be followed until resolution or stabilization of the event(s). Any action taken and follow-up results must be recorded in the patient's medical record. Follow-up laboratory results should be filed with the patient's source documentation and e-CRF. For all AEs that require the patient to discontinue treatment, relevant clinical assessments and laboratory tests should be repeated on at least a monthly basis until final resolution or stabilization of the event(s). These assessments should be captured in the source data and SAE forms but will not be entered in the e-CRF.

All AEs for randomized patients will be recorded in the e-CRF and the patient's source documents. AEs for patients who are screened but not subsequently randomized in the study will be recorded only in the patient's source documents. The following data should be documented for each AE:

- Description of the event;
- Classification of "serious" or "not serious";
- Date of first occurrence and date of resolution (if applicable);
- Severity;
- Causal relationship to study drug(s);
- Action taken;
- Outcome;
- Concomitant medication or other treatment given

An independent DSMB will assess AEs that are reported from study sites. The DSMB will meet at regular intervals throughout the duration of the study or will meet as determined by the DSMB chair, and may recommend systematic treatment arm dose reduction or early termination of the study for safety reasons (see Sections 7.2.4 and 7.2.2).

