12.5.1 Adverse Events

Adverse events will be tabulated with reported incidences by treatment, number of patients that presented adverse events by treatment, serious adverse events by treatment, number of adverse events by body system and by treatment. Summaries will be presented by MedDRA system organ class and preferred term.

For the purpose of analyses and tabulations, AEs will be classified as pretreatment AEs, TEAEs, or post-treatment AEs. More specifically: Pretreatment AE are those that started before the first dose of study drug. TEAE are those that increased in severity or that was appeared at or after the first dose of study drug and before or at the last follow-up, planned for 4 weeks after the last dose of study drug. Post-treatment AEs are those that increased in severity or that appeared after the last follow-up, planned for 4 weeks after the last dose of study drug. For AEs with missing or incomplete start dates, if there is no clear evidence that the AEs started before or after the first dose of study drug, then the AEs will be classified as TEAEs.

AE summary tables will be presented for TEAE only and will include the following: All TEAEs, TEAEs by relationship, TEAEs by maximal severity, TEAEs leading to treatment discontinuation, Serious TEAEs and fatal TEAEs. All AEs, including pre-and post-treatment AEs, will be presented in individual patient data listings.

The number and percentage of patients with at least one AE, as classified by preferred term and system organ class, will be summarized for each treatment group. For these summaries, patients with multiple events will be counted only once per preferred term. AEs will also be summarized by severity and relationship to study drug. At each level of summarization, the event with the highest level of severity or strongest drug relationship will be presented.

All AEs must be listed. In addition, detailed listings will be provided for patients who die, experience a SAE, or discontinue the study because of an AE. These listings will include treatment, patient's age, duration of follow-up, amount of fenretinide received, and time since last intake. Patients who develop Grade 3-4 toxicities will also be listed separately.

A Fisher's Exact test will be used in an exploratory sense to evaluate differences between treatment groups in the incidence of treatment-emergent and clinically significant AEs, graded according to CTCAE outlined in Section 11.1.1.1.

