3.18 Analysis of the Safety Endpoints

For the purpose of analyses and tabulations, AEs will be classified as pretreatment AEs, TEAEs, or posttreatment AEs. More specifically: Pretreatment AE are those that started before the first dose of study drug. TEAE are those that increased in severity or appeared at or after the first dose of study drug and before or at the last follow-up, planned for 4 weeks after the last dose of study

drug. Post-treatment AEs are those that increased in severity or that appeared after the last follow-up, planned for 4 weeks after the last dose of study drug; these AEs will be reported by the Investigator to the sponsor and the appropriate regulatory agency, as well as treated and followed according to local regulations. Post-treatment AE's will be reported separately from the study's clinical study report.

For AEs with missing or incomplete start dates, if there is no clear evidence that the AEs started before or after the first dose of study drug, then the AEs will be classified as TEAEs.

TEAEs will be coded using the Medical Dictionary for Regulatory Activities (MedDRA) and the following information will be summarized:

- Overall TEAEs will also be described according to:
 - Seriousness (yes, no),
 - Severity (mild, moderate, severe, life-threatening),
 - Causality (definitely related, probably related, possibly related, not related),
 - Action taken with study drug (dose not changed, dose interrupted, drug withdrawn, not applicable),
 - Outcome (recovered / resolved, recovered / resolved with sequelae, not recovered / resolved, fatal, unknown).
- The total number of TEAEs, the total number and proportion of patients experiencing at least one TEAE during the treatment period will be summarized by system organ class (SOC) and preferred term (PT). TEAEs occurring with an incidence $\geq 10\%$ will be tabulated in a separate table. To count the number of patients who experience each TEAE, patients experiencing the same TEAE multiple times will only be counted once for the corresponding PT. TEAEs will be tabulated presenting the SOCs alphabetically. All TEAEs, and TEAEs occurring with an incidence $\geq 10\%$, will be presented overall as well as stratified by causality (Definitely Related, Probably Related, Possibly Related, Not Related).
- AE summary tables will be presented for TEAEs only and will include the following:
 - All TEAEs;

- TEAEs by relationship;
- TEAEs by maximal severity;

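### SAP 3.18 reports post-treatment adverse events outside the clinical study report, an undeclared departure from the patient listings that Protocol 12.5.1 requires

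*SAP*

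**What the plan says.** The two documents define the class in the same way. Protocol 12.5.1: "Post-treatment AEs are those that increased in severity or that appeared after the last follow-up, planned for 4 weeks after the last dose". SAP 3.18 repeats that definition.

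They differ on where the events are shown. Protocol 12.5.1 limits the AE summary tables to treatment-emergent AEs (TEAEs) and then adds: "All AEs, including pre-and post-treatment AEs, will be presented in individual patient data listings". It also states that "detailed listings will be provided for patients who die, experience a SAE, or discontinue the study because of an AE", with no restriction to the treatment-emergent period.

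SAP 3.18 keeps the restriction of the summary tables to TEAEs. For post-treatment AEs it says that "these AEs will be reported by the Investigator to the sponsor and the appropriate regulatory agency", and then: "Post-treatment AE's will be reported separately from the study's clinical study report". It does not name the separate report, its timing, or whether events would be shown by arm.

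The only final report that the protocol names is the clinical study report (CSR), in Protocol 20.2. SAP Section 5 tabulates methodological changes from the protocol. Its one entry on safety analysis is the removal of Fisher's exact test.

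**The concern.** Routine AE collection has an end. Protocol 11.1.1: "Adverse events will be collected from the time of informed consent until the last scheduled study follow-up, 4 weeks after the last dose". If an unscheduled safety assessment comes later, collection runs to that instead. Beyond that window, the protocol asks for events suspected to be caused by study drug: the sponsor is to be told of one that he or she who treats the patient "becomes aware of outside of the reporting period until the end of the study that has or is believed to have a causal relationship". The late events that reach the sponsor are therefore largely selected for suspected causality. If they sit outside the CSR, a reader of the safety conclusion cannot see a late suspected reaction beside the evidence on which that conclusion rests. The change is also made without a stated reason.

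**Working it through.** The point rests on no sample size, power or event rate, so the check is a comparison of texts plus arithmetic on study days.

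1. **Same class, different destination.** Both documents take onset or worsening after the last follow-up as the definition. The protocol puts the class in the patient listings. The SAP puts it outside the CSR. With the CSR as the only final report named, the protocol listings most naturally belong there. Protocol 12.5.1 does not say so in words, so this step is an inference.

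2. **Not declared.** The entries in SAP Section 5 cover the exacerbation populations, the healthy control population, the overall exacerbation endpoint, Fisher's exact test, the population on which success is judged, and the Trikafta and pandemic analyses. None concerns post-treatment AEs.

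3. **Start of the class for a completer.** The sixth cycle ends on Day 161 and follow-up is 4 weeks later: 161 + 28 = Day 189, which matches the scheduled end-of-study visit. Post-treatment AEs are those that start or worsen after Day 189.

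4. **Late deaths.** Protocol 11.1.3 counts as an SAE a death after participation but within 30 days post-study if it is suspected to be delayed toxicity. If post-study time is counted from the Day 189 visit (an assumption), this reaches 189 + 30 = Day 219. A death between Day 190 and Day 219 from an event that began or worsened after Day 189 is thus an SAE under the protocol. It is due in the detailed listings of 12.5.1, but falls in the class that SAP 3.18 takes out of the CSR.

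5. **Late worsening.** Protocol 11.1.1 and 11.1.3.1 require ongoing AEs and SAEs to be followed to resolution or stabilisation. A worsening after the last follow-up would then be known to the sponsor, yet it too falls in the removed class.

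6. **What does not move.** The primary safety objective is the incidence of TEAEs. Both documents restrict the AE summary tables to TEAEs. Events up to the last follow-up stay in the CSR under either document.

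**The case against.** The best defence is that the two sentences can both be obeyed. Protocol 12.5.1 speaks of listings without naming the CSR, so a separate listing could satisfy it, and the SAP still sends the events to the sponsor and the regulator. The class is also likely to be small: Protocol 5.4.5.1 expects drug and metabolites to be undetectable within 7-10 days of the last dose, well inside the 4-week window. The mock tables in SAP Section 7 are not part of the available text, so planned listing shells cannot be checked.

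Most of this stands, and it limits the size of the point. It does not remove it. The SAP describes no such listing for these events, and a document outside the CSR does not put them before the reader of its safety conclusion. If the shells do include such a listing for the CSR, the sentence in 3.18 contradicts them and should still go.

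A reader might infer more, in four ways that the documents do not support:

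- *That the events disappear.* They do not; they are reported, but elsewhere.
- *That the primary safety result is affected.* It concerns TEAEs, whose definition and tables are untouched.
- *That Protocol 12.5.1 requires narratives for late serious or fatal events.* It asks for detailed listings.
- *That for early stoppers most of the study falls outside the CSR.* A patient who stops on Day 21 and attends only the 4-week visit has last follow-up on Day 49 (21 + 28), which leaves 189 - 49 = 140 days. But Protocol 8.4 and Section 12 make that single visit the minimum and the full schedule the alternative. A patient who stays on schedule remains in the treatment-emergent period if last follow-up means the actual last visit. For one who leaves, routine collection has ended as well, so the gap comes mainly from the collection window and not from the SAP sentence.

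**Conclusion.** SAP 3.18 is wrong as written, to a minor degree. It departs from Protocol 12.5.1 on where post-treatment AEs are presented, and Section 5 does not record the departure. Followed literally, it keeps out of the CSR a class made up mainly of late events reported because they are believed drug-related, including suspected delayed-toxicity deaths within 30 days post-study. The number of such events cannot be derived from the documents and is probably small. No TEAE count, between-arm comparison, primary result or efficacy analysis changes. The conclusion assumes that the listings in 12.5.1 are meant for the CSR, and that no listing shell outside the available text already restores them.

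**What to change.** Delete the sentence in SAP 3.18 that separates these events from the CSR. Add a patient listing of post-treatment AEs to the CSR, separate from the TEAE output, showing treatment arm and including serious and fatal events. This is consistent with Protocol 12.5.1. Leave the TEAE tables as they are, and leave the reporting route to the sponsor and regulator in place. Because Protocol 11.1.1 has these late events come in by telephone, state which data source the listing draws on. Declaring and justifying the change in SAP Section 5 would close the documentation gap, but would still leave the events out of the CSR, so it is the weaker remedy. The cost is one SAP sentence and one listing.

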7.1.2 Justification for the Primary Endpoints

Primary Efficacy Endpoint: Fenretinide is proposed as an anti-inflammatory therapy with the ability to normalize plasma AA/DHA ratio, and in pre-clinical work, reduce *Pseudomonas* burden. Chronic lung inflammation and infection are at core of the lung destruction over time. Along with safety, it is therefore most relevant to assess the effect of correction of the lipidomic abnormality on FEV₁, a clinically meaningful outcome in CF and the most characterized index for assessing lung function in CF. If indeed fenretinide has positive effects on the immune-inflammatory response, on the function of CFTR and exert anti-infective effect against *PsA*, this will result in a positive absolute difference in the lung function relative to placebo-treated patients, an effect that should be observed over the 6-months duration of the study. Other variables susceptible to be positively affected by an anti-inflammatory and pro-resolving therapy will be evaluated as secondary endpoints.

Safety as a Primary Endpoint: In the proposed study, due to the longer duration of treatment in CF patient, relative to the previous Phase Ib and the increased sample size, these are relevant reasons for nominating safety as a co-primary endpoint, along with assessing efficacy. Similar to the previous study, safety will be assessed during and after the study, taking the screening and baseline status of the patients as a reference. In addition, particular attention will be put on objectively investigating reported symptoms of nyctalopia and/or dermatological disorders, the latter being known class effect of retinoids (including vitamin A). Fenretinide has a very good safety record in other indications at doses superior to the one evaluated in this study, and was shown to be well tolerated in the Phase Ib study with only few adverse events deemed related to the study drug. Still, by administering the study drug over a longer period of time, it is necessary to err on the safe side and continue to build a comprehensive safety database on fenretinide in CF.

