2.3 Study Objectives

2.3.1 Primary Objective:

1. To assess the safety and tolerability of LAU-7b in CF patients by the incidence of treatment emergent adverse events as compared to placebo; and
2. To assess the efficacy of LAU-7b as depicted by the absolute change from Baseline in FEV₁ percent predicted, relative to placebo-treated patients.

2.3.2 Secondary Objectives:

1. To assess the normalizing effect of LAU-7b on the key lipidomic markers in plasma phospholipids, such as AA, DHA and the AA/DHA ratio;
2. To evaluate the efficacy of LAU-7b on other clinically relevant parameters, such as Time-to-first protocol-defined PEx and incidence of protocol-defined PEx, change in weight and BMI, usage of new antibiotics, and the change in CFQ-R;
3. To evaluate the change in selected systemic inflammation markers;
4. Determine if LAU-7b has an effect on lung colonization with *PsA*, as measured by CFU in sputum;
5. To explore the pharmacodynamics of LAU-7b on select systemic metabolipidomic markers, oxidative stress markers, bone formation/resorption, and ceramides subclass concentration;
6. To explore the change in plasma AA/DHA ratio, EPA, inflammation markers and FEV₁ between the start and the end of IV antibiotic treatment for PEx (performed only in patients who receive IV antibiotics for what their treating physician considers a PEx);
7. To explore clinical scoring using the Matouk Disease Score.

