3 STATISTICAL METHODS

3.1 Statistical Handling Policy

3.1.1 Analysis Conventions

This section details general guidelines to be used for the statistical analyses. Deviations from these general policies may be given in the specific detailed sections of this statistical analysis plan. When this situation occurs, the rules set forth in the specific section take precedence over the general conventions. The following policies will be applied to all data presentations and analyses:

- Two-tailed tests will be performed for all analyses that use statistical testing with a significance level of $\alpha = 0.05$
- All p-values will be rounded to 4 decimal places (SAS format p-value). All p-values that round to 0.000 will be presented as '<0.001' and p-values that round to 1.000 will be presented as '>0.999'.
- Summary descriptive statistics will consist of the number and percentage of responses in each category for discrete variables, and the mean, median, standard deviation (SD), minimum, maximum, and 95% confidence interval for continuous variables.
- All mean and median values will be formatted to one decimal place. Standard deviation values will be formatted to two decimal places.
- All percentages will be rounded to one decimal place. Where appropriate, the number and percentage of responses will be presented in the form XX (XX.X %), where the percentage is in the parentheses.
- All listings will be sorted for presentation in order of treatment group, site number, subject number, and date of procedure or event.
- When necessary for analysis purposes, partial dates will be completed (i.e., turned into complete dates) using the most conservative approach. Where appropriate, all analyses and summary tables will have the population sample size for each treatment group in the column heading.

- Tables will include titles with the corresponding analysis population and footnotes describing the analyses involved, and listings of covariates included in the analyses, where relevant.
- In order to maintain vertical alignment, all tables and listings will be incorporated into MS Word and an 8-point Courier New font will be used.
- Version 9.4 (or later) of SAS® will be the statistical software package used to produce all summaries, listings, statistical analyses, and graphs.
- Version 20.0 (or higher) of MedDRA will be used for adverse event and pre-treatment conditions coding.

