5 METHODOLOGICAL CHANGES FROM PROTOCOL

SAP Version (date)	Relevant Section in Protocol (Amendment 3 – dated: 31JUL2019)	Section (s) and Change (s) in SAP	Rationale for Change
Final v5.0 (dated: 08OCT2019)	Protocol Section 12.2 (Analysis Population); PEx Analysis Subset Population	SAP Section 3.3. (Analysis Population): 2 separate PEx Analysis Populations have been defined: 1) Protocol-Defined PEx Population (patients who experience a PEx with $\geq 4/12$ positive Fuch symptoms and treated with an IV antibiotic); 2) Overall PEx Population (patients who experience a PEx treated with an oral or IV antibiotic). This differs from the Protocol, wherein only one PEx Population, defined by patients treated with an IV antibiotic, is defined	To distinguish between PEx defined by Investigators based on clinical judgment and PEx defined by a standard criteria.
Final v5.0 (dated: 08OCT2019)	Protocol Section 12.2 (Analysis Population)	SAP Section 3.3. (Analysis Population): Addition of a definition of the Healthy Control Population used for the first secondary parameter.	To define the Healthy Control Population to be used in the assessment of pharmacodynamic parameters (AA, DHA and AA/DHA ratio)
Final v5.0 (dated: 08OCT2019)	Protocol Section 6 (Study Objectives-Secondary Objectives); Protocol Section 7.1.3 (Secondary Endpoints)	SAP Section 3.15 (Analysis of Secondary Endpoints): assessment of Overall PEx has been added, in addition to the assessment of Protocol-Defined PEx	To distinguish between PEx defined by Investigators based on clinical judgment and PEx defined by a standard criteria.
Final v5.0 (dated: 08OCT2019)	Protocol Section 12.5.1 (Adverse Events), 12.5.2 (Clinical Laboratory Assessments)	SAP Section 3.18 (Analysis of the Safety Endpoints): removal of the methodology related to the Fisher's Exact test to assess between-group differences in treatment emergent and clinically significant AEs	This phase 2 trial was not designed to test specified hypotheses about safety. Therefore, the Fisher's exact test will not be performed. AEs will be presented descriptively, and a qualitative evaluation will be performed.

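### The primary, placebo-compared safety objective has no planned between-arm estimate or interval for treatment-emergent adverse events

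*SAP*

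**What the plan says.** SAP 2.3.1 (and Protocol section 6) states the first primary objective as: "To assess the safety and tolerability of LAU-7b in CF patients by the incidence of treatment emergent adverse events as compared to placebo". Protocol 7.1.2 gives reasons for "nominating safety as a co-primary endpoint".

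Protocol 12.5.1 tabulates adverse events by treatment and adds one between-arm tool: a Fisher's "Exact test will be used in an exploratory sense to evaluate differences between treatment groups". Protocol 12.5.2 does the same for laboratory toxicities.

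SAP section 5 records that this test was removed at v5.0 (8 October 2019), because the Phase 2 trial was not designed to test specified safety hypotheses. In its place: "AEs will be presented descriptively, and a qualitative evaluation will be performed".

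SAP 3.18 then lists the TEAE output: "The total number of TEAEs, the total number and proportion of patients experiencing at least one TEAE during the treatment period will be summarized". The tables are arranged by MedDRA class and term, with breakdowns by seriousness, severity, causality, action taken and outcome. For descriptive summaries in general, SAP 3.1.1 provides "the number and percentage of responses in each category for discrete variables". It names a 95% confidence interval only for continuous variables. SAP 3.8 and 3.10 state that no statistical analyses are planned for vital signs, ECG or ophthalmologic data.

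**The concern.** The objective asks a comparative question: is TEAE incidence on LAU-7b different from placebo, and by how much? The SAP text produces the two proportions that go into the answer but not the difference between them, and nothing shows how precisely that difference is known.

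At this sample size the imprecision is large. Two similar percentages can look reassuring while the data remain compatible with a sizeable excess on LAU-7b. This matters most for serious, ocular and skin events: the protocol singles out the latter two for attention, and their counts may be small. Without an interval, the report on one of the two primary objectives gives no statement of what size of harm has and has not been ruled out.

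**Working it through.** **Inputs**
- Patients randomised: at least 136, allocated 1:1 (SAP 2.4 and 2.6), so 136 / 2 = 68 per arm.
- The plan's own figure reproduces: 2 x 60 = 120 completers; 120 / (1 - 0.10) = 133.3, rounded up to 134; the next multiple of 8 is 136. It comes from the FEV1 endpoint. No sample size, margin or power is stated for safety.
- Every randomised patient who takes at least one dose is in the safety population (SAP 3.3), so 68 per arm is used below.
- Event counts are assumptions, because the documents give no expected TEAE rates.

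**Method for the risk difference.** Newcombe interval. With p1 and p2 the observed proportions on LAU-7b and placebo, and (l1, u1) and (l2, u2) their 95% Wilson limits:
- lower limit = (p1 - p2) - sqrt[(p1 - l1)^2 + (u2 - p2)^2]
- upper limit = (p1 - p2) + sqrt[(u1 - p1)^2 + (p2 - l2)^2]

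**Case 1: identical rates, 12/68 in each arm (17.6%).** Wilson limits are 10.4% and 28.4% in both arms.
- Half-width = sqrt[(17.65 - 10.39)^2 + (28.36 - 17.65)^2] = sqrt[52.7 + 114.7] = 12.9 points.
- 95% CI: -12.9 to +12.9 points.

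**Case 2: 6/68 (8.8%) against 3/68 (4.4%).** Wilson limits are 4.1% to 17.9% and 1.5% to 12.2%. The difference is 4.4 points.
- Lower = 4.41 - sqrt[(8.82 - 4.11)^2 + (12.19 - 4.41)^2] = 4.41 - 9.09 = -4.7.
- Upper = 4.41 + sqrt[(17.94 - 8.82)^2 + (4.41 - 1.51)^2] = 4.41 + 9.57 = +14.0.

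**Identical rates across a range of assumed counts**

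| Events in each arm | Observed rate | Upper 95% limit for the difference |
|---|---|---|
| 3/68 | 4.4% | +8.3 points |
| 7/68 | 10.3% | +10.8 points |
| 12/68 | 17.6% | +12.9 points |
| 14/68 | 20.6% | +13.6 points |

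**Case 3: no events in 68 patients on LAU-7b.** The exact upper bound on the true rate solves (1 - p)^68 = a.
- One-sided 95%: 1 - 0.05^(1/68) = 4.3%.
- Two-sided 95%: 1 - 0.025^(1/68) = 5.3%.
- Put the other way, an event with a true rate of 2% has a 0.98^68 = 25% chance of not appearing at all.

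**Would restoring the Fisher test close the gap?** No. With 5/68 against 0/68 the test gives p = 0.058, and the p-value alone says nothing about size. The Newcombe interval for the same data is +0.6 to +16.1 points. The missing piece is the estimate with its interval.

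**The case against.** Descriptive adverse event tables are a defensible choice in a Phase II trial sized on FEV1. Counts and percentages were already the protocol's main adverse event output. The dropped test was labelled exploratory, and its removal is disclosed with a reason. Study success rests on FEV1 alone (SAP 3.2 and 3.14), so no formal claim depends on the adverse event table. A reader given the counts and denominators can compute the intervals. All of this stands, and it is why the point is an improvement to reporting and no threat to the trial's main result. It does not explain why a comparative primary objective should be reported without its own comparison.

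The plan is also not empty on between-arm safety. SAP 3.18 lists pulmonary exacerbation incidence and antibiotic requirement among the safety evaluations, and SAP 3.15 compares both by count and time-to-event models. SAP 3.10 tabulates night-vision symptoms by arm, with objectively confirmed cases shown separately. SAP 3.19 gives the DSMB unblinded active-versus-placebo safety analyses. None of these yields a TEAE risk difference in the final report.

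Three stronger readings are tempting and are not supported:
- A reader might infer that the test was withdrawn late. SAP section 5 dates the removal to v5.0 in October 2019, and the v6.0 changes listed in SAP section 6 do not touch safety.
- A reader might infer that the protocol would conclude safety from a non-significant Fisher result. Neither document ties a safety conclusion to that p-value.
- A reader might infer that an unremarkable table will be declared proof of safety. The protocol hypothesises that treatment will be safe and well tolerated, but neither document says how the table will be worded into a conclusion.

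Finally, the mock tables in SAP section 7 were not available. An interval column may exist there, so the absence is established only for the text of SAP 3.18 and 3.1.1.

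**Conclusion.** The point holds as a gap in the written methods. For a primary objective defined as TEAE incidence against placebo, the SAP text specifies frequencies and a qualitative evaluation, with no between-arm estimate and no interval. The stated reason for removing the Fisher test supports having no p-values and does not bear on estimation.

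The size is material. At 68 per arm, equal observed rates between about 4% and 21% leave an excess of roughly 8 to 14 points on LAU-7b inside the 95% interval, and a zero count leaves a true rate of 4.3% (one-sided) or 5.3% (two-sided) possible. These figures rest on assumed event counts and on the stated minimum enrolment; a larger trial would narrow them. They show what the data could leave open. They do not suggest that LAU-7b causes harm.

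**What to change.** In SAP 3.18, add one table on the safety population giving the LAU-7b minus placebo risk difference with a Newcombe or exact 95% CI, without p-values, for patients with:
- any TEAE;
- a serious TEAE;
- a TEAE leading to treatment discontinuation;
- an ocular TEAE, including night blindness;
- a skin TEAE.

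State that the upper limits will be reported alongside the qualitative safety evaluation. No margin is proposed, so the limits inform the wording and do not act as a pass/fail rule. If the mock tables already hold such a column, it is enough to name the method in 3.18.

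The cost is a short SAP addition and one table from data already collected, with no extra patients, visits or alpha. The downside is that wide intervals will make the safety statement more cautious.
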